## 7.3.4 Screening Lead-In and Baseline

Upon signing the informed consent form, subjects will begin the screening lead-in period of 14-days minimum. No data will be collected from the subject during this time; however, the data collected during pre-screening will be saved in ePRO as study eligibility data.

After 14 days of lead-in time, subjects will be prompted to retake the BDI-II and PHQ-9 assessments in ePRO. Subjects will also take a QIDS-SR assessment in ePRO. A subject must have a BDI-II score between 20 and 63, indicating moderate to severe MDD, at both initial pre-screening and baseline to participate in the study.

If the BDI-II assessment score is not within the moderate to severe MDD range, the subject's health will be considered insufficiently stable for study entry. The subject will be notified that they are no longer eligible for study participation and they will be considered a screen failure.

If the screened subject's data is within the moderate to severe MDD range for the BDI-II assessment, the subject will advance to scheduling a meeting with a clinician from the investigative team.

7.3.5 Clinical Interview and Eligibility Reevaluation

Subjects with baseline BDI-II scores within the range of moderate to severe MDD will be contacted to schedule a meeting with a clinician from the investigative staff.

During this teleconference or video conference with the subject, the clinician will conduct the M.I.N.I. and DSM-5 assessments to evaluate the subject for moderate to severe MDD. If the clinician determines that the subject cannot be diagnosed with moderate to severe MDD, the subject will be deemed a screen failure and discontinued from study participation. Subjects who have or appear to have any of the following diagnoses or conditions will also be excluded from further study participation and documented as a screen failure:

- Bipolar I disorder
- Bipolar II disorder
- Other specified bipolar and related disorder
- Panic disorder
- Agoraphobia
- Social anxiety disorder (social phobia)
- Obsessive-compulsive disorder
- Posttraumatic stress disorder
- Alcohol use disorder in the past 12 months
- Substance use disorder (non-alcohol) in the past 12 months
- Any psychotic disorder (e.g., schizophrenia, schizoaffective disorder)
- Major depressive disorder with psychotic features
- Anorexia nervosa

- Bulimia nervosa
- Binge-eating disorder
- Generalized anxiety disorder
- Any cognitive or developmental disorder (e.g., autism, Down's Syndrome)
- Any personality disorder or psychiatric disorder that may interfere with study participation

Subjects who meet moderate to severe MDD criteria per the M.I.N.I. and DSM-5 assessment will be diagnosed as having moderate to severe MDD by the clinician.

After confirming a diagnosis of moderate to severe MDD for the subject, the clinician will review the subject's reported information in ePRO to ensure the subject continues to meet study eligibility criteria. Any subject who fails to fulfill any element of the inclusion and exclusion criteria will be considered a screen failure.

Subjects who meet all study eligibility criteria and receive a diagnosis of moderate to severe MDD from the clinician will advance to receiving a prescription for an investigational device to be used during the study.

# 7.3.6 Subject Identification and Randomization

Once eligibility is confirmed by the clinician and a prescription is written for the investigational device, the subject will be assigned a unique identification (ID) number by Climb. The subject ID number will consist of 01 for the first subject, 02 for the second subject, and so on. This number will be used to identify the subject during their participation in the study. Climb will maintain a log of all subjects enrolled in the clinical study including their names, their study ID number, and contact information.

The subject will also be randomized (approximately 1:1) to either the treatment group (active device) or the control (sham device). Climb will create and maintain the randomization table and assign subjects to each group. The randomization data will be restricted to unblinded investigative staff members only until the conclusion of the study. The unblinded team will be responsible for maintaining the randomization table.

#### 7.3.6.1 **Device Shipment**

An unblinded investigative staff member who is not associated with any other function of the study will receive the subject's randomization allocation and contact/shipping address information. The study device type, either sham or active treatment, assigned to the subject through the randomization process will be directly shipped to the location requested by the subject by a third party vendor in collaboration with the unblinded investigative staff member.

# 7.3.7 Subject Training

The subject will be advised to not use the investigational device until after receiving live training. Prior to the live training, the subject will be asked to complete online device training using pre-recorded videos.

Once the subject receives the investigational device, they must participate in a live training with investigative staff to further learn how to correctly place and use the device, clean the device components that will be reused, and complete data collection in ePRO. The trainer will explain that the device is locked

CES-MDD	Version 5.0
FW-200-05	08-Jun-2022

at Level 2 and that the subject may or may not feel a sensation of stimulation, regardless of whether the device is a placebo or active device.

The subject will confirm in ePRO that their training was completed. The trainer will also record in ePRO that training was completed. The subject will continue to have access to the pre-recorded instructional video and usage manual during the study as needed for additional reference and may contact the investigative staff for device handling support during the study.

# 7.3.7.1 James Blinding Index

After participating in the live device training session with investigative staff, the subject will be asked in ePRO which type of investigational device they believe they received (active device or control). The subject will select from 5 options to indicate if they strongly believe they have an active device, somewhat believe they have an active device, or strongly believe they have a sham device, or strongly believe they have a sham device. The subject's response will be analyzed using the James Blinding Index.

# 7.3.8 Period 1: Week 1 Device Usage

Subjects will begin using the investigational device the day after the live training session with investigative staff. Subject will use the device as instructed, for 20 minutes after waking for the day and for 20 minutes prior to going to bed. Each day of study therapy, subjects will report in ePRO whether or not they used the study device as instructed and if there had been a change to their health status or medications over the previous 24 hours.

# 7.3.9 Period 1: Week 1 Evaluation

After completion of at least 1 week (7 days plus up to 2 additional days) of device usage, subjects will be requested to complete the following in ePRO:

- BDI-II
- PHQ-9
- QIDS-SR
- Any Adverse Events
- Any changes to their reported concomitant medications

# 7.3.10 Period 2: Week 2 Device Usage

Subjects will continue daily use of the device and report in ePRO whether or not they used the study device as instructed and if there had been a change to their health status or medications over the previous 24 hours.

# 7.3.11 Period 2: Week 2 Evaluation

After completing Week 2 (7 days plus up to 2 additional days) of device usage, subjects will be requested to complete the following in ePRO:

- BDI-II
- PHQ-9
- QIDS-SR
- Any Adverse Events
- Any changes to their reported concomitant medications

#### 7.3.12 Period 3: Weeks 3-4 Device Usage

Subjects will continue daily use of the device and report in ePRO whether or not they used the study device as instructed and if there had been a change to their health status or medications over the previous 24 hours.

#### 7.3.13 End of Therapy: Week 4 Evaluation

After completion of at least 4 weeks (28 days plus up to 5 additional days) of device usage, subjects will be requested to detail or answer the following in ePRO:

- BDI-II
- PHQ-9
- QIDS-SR
- Any Adverse Events
- Any changes to their reported concomitant medications

At End of Therapy, subjects will be contacted to return the study device to the unblinded Sponsor representative. Investigative staff will verify all subject data has been completed and exit the subject from the study.

#### 7.3.14 Unscheduled Visits

Should a subject be withdrawn early from the study, investigative staff will ask the subject to report the adverse event in ePRO (if applicable), and complete the following assessments:

- BDI-II
- PHQ-9
- QIDS-SR

The investigative staff will also assist the subject in returning the investigational device.

#### 7.3.15 Criteria and Procedures for Subject Withdrawal or Discontinuation

7.3.15.1 Subject Withdrawal and Discontinuation

During the course of this clinical investigation, subjects will be or may elect to withdraw from further treatment.

CES-MDD	Version 5.0
FW-200-05	08-Jun-2022

All subjects discontinued from the clinical investigation due to an unexpected adverse device effect, directly related to the clinical investigation, will be followed by investigative staff to the best of their ability until the effect resolves, or reaches a stable condition, in case of the undesirable event of an occurred permanent impairment. Investigative staff will document in ePRO the date and reason(s) for subject withdrawal. All subjects who discontinue treatment for any reason shall be contacted by investigative staff in an effort to follow the subject for safety.

Subjects have the right to withdraw from the study at any time and for any reason without prejudice to their future medical care by the study personnel or institution. If a subject decides to withdraw, all study evaluations and procedures will be stopped, and an inquiry will be made about the cause of withdrawal. Climb will account for and document all subjects enrolled in the study, including those withdrawn from the study or lost to follow-up. If a subject withdraws from the clinical investigation, the reason(s) shall be reported in ePRO.

Reasons for withdrawal include, but are not limited to:

- Subject's rescission of consent.
- Any unexpected adverse device effect which is, in the opinion of the Principal Investigator, related to the device and will endanger the wellbeing of the subject if the treatment is continued.
- The development of any undercurrent illness(es), infection or condition(s) that might interfere with the Clinical Investigation Plan.
- Any problem deemed by the Principal Investigator and Sponsor to be sufficient to cause discontinuation.
- Lost to follow-up
- Death

Additional study data may no longer be collected after the point at which a subject has been withdrawn from the study or withdraws his/her consent. Data collected up to the point of subject withdrawal will be used for analysis.

Subjects who are withdrawn will not be replaced if they have received the investigational device. If possible, any assessments planned for the subject on withdrawal from the clinical investigation, including adverse event collection, should be performed when intention to withdraw the subject is announced.

Subjects who are withdrawn prior to receiving an investigational device will be replaced, including screen failures.

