If the screened subject's data is within the acceptable range for the BDI-II, the subject will advance to scheduling a meeting with a clinician from the investigative team. Via teleconference, the clinician will administer the M.I.N.I. assessment and the Diagnostic and Statistical Manual of Mental Disorders (DSM-5) evaluation.

If the clinician identifies that the subject's results do not meet both M.I.N.I. and DSM-5 criteria for moderate to severe MDD, the subject will be notified that they are no longer eligible for study participation. Additionally, during the live interview, the clinician may deem the subject a screen failure should they no longer meet all inclusion criteria or meet any exclusion criteria.

If the clinician diagnoses the subject with moderate to severe MDD based on the results of the M.I.N.I. and DSM-5 assessments, and determines that the subject meets all other eligibility criteria, the subject will be prescribed study treatment by the clinician and be randomized to a study treatment arm (sham device or active treatment device). Only eligible subjects will be enrolled in the study, randomized to a treatment arm, and receive an investigational device shipped directly to them by an unblinded Sponsor designee.

Prior to starting self-administered therapy with the FW-200 sham or active device, subjects will review an online device training video and undergo a live device and ePRO training with investigative staff. The day after successfully completing live training with investigative staff, subjects will begin self-administered therapy twice per day, one 20-minute session after waking for the day and one 20-minute session before going to bed. Each day of study therapy, subjects will confirm in ePRO that they completed both treatment sessions for the day. Subjects will also be asked if there have been any changes to their medications or health status within the past 24 hours. This will be captured as free text to allow subjects to describe any positive or negative (adverse events) experiences during study therapy.

At the following time points, subjects will retake the BDI-II, PHQ-9, and QIDS-SR assessments:

- Week 1 (Day 7 of therapy)
- Week 2 (Day 14 of therapy)
- Week 4 (Day 28 of therapy)

For the Week 1 and Week 2 evaluations, subjects will have 2 additional days to complete the assessments. For the Week 4 evaluation, subjects will have 5 additional days to complete the assessments. Should a

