subject complete one of these assessments outside the allowed time window, this instance will be documented as a minor protocol deviation. Subjects will not be withdrawn from the study for minor protocol deviations.

Subject participation in the study concludes after completion of the Week 4 evaluation. At that time, subjects will be contacted to return the investigational device and log in ePRO any adverse experiences or medication changes within the past 24 hours.

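### Section 7.3.15.1 lets data collection end when a subject is withdrawn for stopping the device, even if consent stands, so a Week 2 BDI-II needed for the intent-to-treat analysis can be lost

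*Combined protocol and SAP*

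**What the plan says.** Section 7.3.15.1 opens by saying that "subjects will be or may elect to withdraw from further treatment". For those who stop treatment it provides: "All subjects who discontinue treatment for any reason shall be contacted by investigative staff in an effort to follow the subject for safety".

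Its list of withdrawal reasons, which is not exhaustive, has six entries. Three are rescinded consent, loss to follow-up and death. The other three are events that stop the device:

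- "Any unexpected adverse device effect which is, in the opinion of the Principal Investigator, related to the device", where continuing treatment would endanger the subject;
- an illness, infection or condition that might interfere with the investigation;
- "Any problem deemed by the Principal Investigator and Sponsor to be sufficient to cause discontinuation".

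On data collection the section says "If a subject decides to withdraw, all study evaluations and procedures will be stopped", and later "Additional study data may no longer be collected after the point at which a subject has been withdrawn from the study". That last sentence goes on to name withdrawal of consent as a separate alternative. The section then says that data gathered up to withdrawal will be analysed.

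Section 7.3.14 asks for BDI-II, PHQ-9 and QIDS-SR when a subject is withdrawn early. The end of 7.3.15.1 places planned withdrawal assessments, if possible, at the time the intention to withdraw is announced.

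The primary endpoint is the BDI-II change at two weeks (Section 6.2.1). The primary analysis is intent-to-treat, whatever treatment was received (Section 8.1). Missing data are to be multiply imputed (Section 8.3), with details left to a standalone SAP (Section 8) that is not among the documents supplied.

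**The concern.** An analysis that keeps subjects as randomized, whatever treatment they received, needs the Week 2 score from subjects who stopped the device as much as from those who continued. In this trial that score is a self-report questionnaire answered remotely, so stopping the device does not in itself prevent a subject from giving it.

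The withdrawal section nevertheless treats several device-stopping events as grounds for leaving the study, and leaving the study as a point at which collection may end. Where that happens before Day 14, the primary outcome is left to imputation. Subjects who stop because of a device effect, an illness or a problem may well differ from the rest of their arm. A later SAP can choose the imputation model but cannot recover a score that nobody requested.

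**Working it through.** The plan gives no figure on this point, so the check sets the sections side by side.

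**Step 1: which listed reasons leave a recoverable score?** Inputs: the six reasons in Section 7.3.15.1.

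| Reason | Can consent still stand? | Could the subject still answer? |
|---|---|---|
| Consent rescinded | No | Not to be asked |
| Related device effect | Yes | Possibly |
| Intervening illness or condition | Yes | Possibly |
| Problem judged by Principal Investigator and Sponsor | Yes | Possibly |
| Lost to follow-up | Yes, but not reachable | No |
| Death | Not applicable | No |

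Three of the six can remove a subject who is still willing and able to answer.

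**Step 2: does the text allow collection to stop for those three?** Yes. The sentence on further data joins study withdrawal and withdrawal of consent with "or", so study withdrawal alone is enough. Its verb is permissive: it does not forbid later collection, but nothing requires it. The sentence on subjects who stop treatment names safety follow-up and no efficacy assessment.

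**Step 3: does the exit assessment fill the gap?** Inputs: Week 1 is Day 7 + 2 days and Week 2 is Day 14 + 2 days, counted from Day 0, the first day of use (Section 7.3.1). The withdrawal days below are illustrations.

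- Withdrawn on Day 5: an exit score at about Day 5, with no assured Week 1 or Week 2 score.
- Withdrawn on Day 10: a Week 1 score and an exit score at about Day 10, with no assured Week 2 score.
- Withdrawn on Days 14 to 16: the exit score falls inside the Week 2 window.

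So the exposure is confined to withdrawal before Day 14. There, the exit score is earlier than the endpoint requires. Sections 7.3.14 and 7.3.15.1 also do not state how the exit assessments fit with the instruction to stop all evaluations when a subject decides to withdraw.

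**Step 4: does the visit wording settle it?** No. Section 7.3.1 counts visits from first use. Sections 7.3.9, 7.3.11 and 7.3.13 make the Week 1, 2 and 4 requests follow a completed period of device usage, a condition that a subject who has stopped does not literally meet.

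**Step 5: can the bias be sized?** For one arm, the shift in the estimate is w × d × (1 − r). Here w is the share of the arm missing after stopping, d is the mean difference in improvement between missing and observed subjects, and r is the share of d that imputation recovers. The documents give none of the three. If the missing subjects did worse and r is below 1, the effect is overstated when they are in the active arm and understated when they are in the sham arm. Losses in both arms partly offset. If r = 1 there is no shift.

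**The case against.** The strongest reply is that a subject who merely stops the device is probably meant to stay on schedule. Visits are counted from first use. Sections 7.3.8, 7.3.10 and 7.3.12 have subjects report daily whether or not they used the device. Section 15.2.1 records discontinuation of treatment as an action taken for an adverse event without linking it to study exit. Section 7.1.1 adds "Subjects will not be withdrawn from the study for minor protocol deviations". The safety-contact sentence does not say that contact is for safety alone.

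Most of this stands. A reader might infer that everyone who stops the device loses the Week 2 score; the documents do not support that. For the subject who simply stops, the undefined terms are mainly a clarity gap, although no section states that assessments continue. The only examples given of minor deviations concern assessments, so it is open whether non-use of the device counts as one.

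The safeguards are also real: the exit BDI-II, the Week 1 score, the use of data up to withdrawal, and multiple imputation. The exposed group is narrow, since wording cannot recover scores after rescinded consent, loss to follow-up or death. The imputation model cannot be criticised without the standalone SAP.

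None of this answers the case of a subject withdrawn from the study before Day 14 for a device effect, an illness or another judged problem, with consent intact. For that subject the text permits collection to end, and no safeguard yields a Day 14 score.

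**Conclusion.** The point holds for subjects withdrawn from the study before Day 14 because the device was stopped, who have not withdrawn consent and could still answer. For them the protocol permits the loss of a primary-outcome score that its own analysis population calls for. This should be fixed, but it does not invalidate the design.

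The size and direction of any bias cannot be determined from the documents, which give no rate of stopping or withdrawal before Week 2 and no imputation model. Two stronger readings should be resisted.

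- A reader might size the loss from the prior remote trial in Section 4.2, where 83 + 78 = 161 of 275 subjects completed the 4-week assessments. That figure is all-cause, relates to Week 4, and comes from a trial that also enrolled mild depression. It says nothing about Week 2 scores lost after stopping the device.
- A reader might infer that the loss favours the active device. The sign depends on which arm loses more subjects and how they fared, and neither is known.

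The conclusion assumes that no document outside those supplied already instructs staff to continue the questionnaires.

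**What to change.** In Section 7.3.15.1, separate (a) stopping the device, by the subject's own choice or by decision of the Principal Investigator or Sponsor, from (b) withdrawing consent to further data collection. Then:

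- state that subjects in (a) who have not withdrawn consent are still asked for BDI-II, PHQ-9 and QIDS-SR at Weeks 1, 2 and 4, timed from Day 0;
- state that the Week 2 BDI-II collected this way is used in the primary analysis, so that only scores that are truly missing are imputed;
- limit the sentence ending data collection to (b), accepting loss to follow-up and death as unavoidable losses;
- align the device-usage wording in 7.3.9, 7.3.11 and 7.3.13 with the schedule in 7.3.1;
- reconcile 7.3.14 and 7.3.15.1 on which exit assessments are done and when.

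When or why a subject stops the device is unchanged, and any subject may still withdraw consent.

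The cost is a protocol amendment with IRB approval (Section 10) and a small questionnaire burden for subjects who have stopped. The documents do not describe how the ePRO handles prompts after withdrawal, so that setting needs checking. No new instrument or visit is needed. The resulting estimate may be less favourable to the device.

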# 7.3.1 Schedule of Assessments

Assessments and Device Activities	Recr	uitment			Enrolment			Period 1	Period 1 Eval	Period 2	Period 2 Eval	Period 3	ΕΟΤ	Unschedu led
Activity	Pre- Screening	Consent and Eligibility c	Screening Lead-In Start	Screening Lead-In Complete / Baseline	Clinical Interview / Reevaluation c	Diagnosis / Randomi zation	Subject Training c	Week 1 Device Usage	Week 1 Eval	Week 2 Device Usage	Week 2 Eval	Weeks 3- 4 Device Usage	Week 4 Eval	Safety / Unsche duled
Timeline / Window (Days)	Prior to Informed Consent	After Initial Pre-Screen and before Lead-In	Start of Lead-In, Minimum 14 Days before baseline	Minimum 14 Days to complete Lead-In	Prior to Day 0	Prior to Day 0	Prior to Day 0	Day 0 +7 [first day of use and continui ng for 7 days] d	Day 7 + 2 days	Days 814	Day 14 + 2 days	Day 15 – 28	Day 28 +5 days	N/A
Inclusion / Exclusion criteriaª	Х		Х											
Demographics	X		X											
Beck Depression Inventory-II (BDI-II)	X		X	X					Х		X		х	X

CES-MDD
FW-200-05

Personal Health Questionnaire Depression Scale (PHQ-9)	X		X	Х			X	Х	X	Х
Mini- International Neuropsychiat ric Interview	Х		Х		X°					
-	•				-					
(MINI) questions										
Concomitant Medications	Х		Х					Х	Х	
Medical History	Х		Х							
Informed Consent		Х								
Eligibility Evaluation b		Х			Х					
Quick Inventory of Depressive Symptomatolo gy-Self Report (QIDS-SR)				Х			X	X	X	Х

DSM-5 Interview			х									
DSM-5 Diagnosis				Х								
Randomizatio n				Х								
Device Training					Х							
-		-										
Device Usage/Diary						Х		х		Х		
Device Return											Х	X (if applicable )
Adverse Events						X	Х	X	Х	X	Х	X

CES-MDD	Version 5.0
FW-200-05	08-Jun-2022

a Inclusion/Exclusion Criteria during Pre-Screening within the Recruitment Phase includes the potential subject's ability to meet inclusion or exclusion criteria that do not require assessment by a clinician from the investigative staff.

b Eligibility Evaluation occurs after informed consent is signed. This includes review of all potential subject data received to determine if inclusion criteria are met and no exclusion criteria are met. c Study Activity that requires telephone contact with the candidate subject/subject. d Day 0 is defined as the first day of the subject's self-administered treatment. e Complete M.I.N.I. interview conducted by the clinician with the subject.

Version 5.0 08-Jun-2022

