# **8.3** ANALYTICAL PROCEDURES

The primary endpoint is the change in BDI-II at week 2 compared to baseline. Analysis will be based on a linear model for change, adjusted for each subject's baseline value. The mathematical statement of the null and alternative hypothesis for primary endpoint is:

Ho: B2  $\leq 0$ 

Ha: B2 > 0 where B2 represents the regression coefficient from the linear model corresponding to study arm, parameterized so a regression coefficient greater than zero represents a greater mean change for the treatment group compared to the control group. The general form of the linear model for each endpoint is:

 $\Delta Y = B0 + B1Y0 B2*X$ 

where  $\Delta Y$  is the change in outcome from baseline at week 2, B0 is the intercept term, B1 is the coefficient for the subject's baseline value Y0, and X is the treatment group indicator (1 = treatment, 0 = sham). Multiple imputation will be employed to address missing data.

Study success will be based on successful rejection of the null hypothesis for the primary endpoint.

Subgroup analysis will be provided based on sex and race as well as potentially other baseline factors, including baseline BDI-II score.

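### The protocol gives conflicting instructions on whether a subject who chooses to withdraw completes a last BDI-II, and does not say how such a score would inform the Week 2 analysis

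*Combined protocol and SAP*

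**What the plan says.** Four places in the protocol bear on the moment of withdrawal.

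- Section 7.3.15.1, on a subject's own decision to leave: "If a subject decides to withdraw, all study evaluations and procedures will be stopped". The sentence goes on to ask for the cause of withdrawal.
- Section 7.3.14: "Should a subject be withdrawn early from the study, investigative staff will ask the subject to report the adverse event in ePRO" where applicable, and to complete the BDI-II, PHQ-9 and QIDS-SR.
- Section 7.3.1: the schedule marks all three questionnaires in the Safety/Unscheduled column.
- The closing part of 7.3.15.1: "If possible, any assessments planned for the subject on withdrawal from the clinical investigation, including adverse event collection, should be performed", at the time the intention to withdraw is announced.

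On use of the data, 7.3.15.1 says "Data collected up to the point of subject withdrawal will be used for analysis", and that further data may not be collected once the subject is out. The primary endpoint is the change in BDI-II from baseline to Week 2 (6.2.1), with a window of Day 14 plus 2 days (7.1.1). Section 8.3 gives a model with baseline and arm and adds "Multiple imputation will be employed to address missing data", without an imputation model. Section 8 leaves missing-data detail and sensitivity analyses to a standalone SAP, which is not among the documents supplied.

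**The concern.** A staff member holding the protocol cannot tell whether to ask a subject who has just decided to leave for a last set of questionnaires. One sentence says evaluations stop; three other places say the questionnaires are due. If the stopping sentence is followed as written, exit scores will exist for subjects whom staff withdraw and be absent for those who choose to go. They would then be missing according to the reason for leaving.

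For a subject who leaves before Day 7, the exit BDI-II is the only post-baseline outcome the trial could have. Without it, imputation for that subject can draw on little beyond baseline and arm. If poor response drives leaving more in one arm than in the other, the Week 2 comparison is biased, and the score that would have revealed the poor response was not collected.

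**Working it through.** **The passages side by side**

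| Place | Who | Last BDI-II? |
|---|---|---|
| 7.3.15.1, stopping sentence | a subject who decides to withdraw | no, evaluations stop |
| 7.3.14 | a subject who is withdrawn early | yes, requested |
| 7.3.1, Unscheduled column | not stated | yes, marked |
| 7.3.15.1, closing part | a subject being withdrawn | yes, if possible |

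The list of withdrawal reasons in 7.3.15.1 mixes subject-initiated reasons (rescinded consent) with investigator-initiated ones. The protocol therefore never separates the two cases.

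**The plan's own figure.** Section 8.5 assumes a difference of 3.2, SD 9, two-sided alpha 0.05 and 80% power. n per arm = 2 × (1.960 + 0.842)² × 9² / 3.2² ≈ 124.2, rounded up to 125, so 250 in total. This reproduces. The planned standard error is 9 × √(2/125) = 1.14 points.

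**Scale of dropout.** Section 8.5 expects some missing data but gives no rate. In the previous FW-200 trial (4.2), 83 of 137 and 78 of 138 completed Week 4. Non-completion was 54/137 = 39.4% (active) and 60/138 = 43.5% (sham), or 114/275 = 41.5% overall. No Week 2 figure is given, so 11%, 20% and 29% are taken as an assumed range.

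**Illustrative simulation.** Stated design: 125 per arm, true difference 3.2, SD 9. Assumed: Week 1 to Week 2 residual correlation 0.75; all dropout before Week 1; in the active arm, dropout odds rise by a factor of e per SD of worse response; in sham, dropout is unrelated to response. Each exit score is treated as a Week 1 score and used in regression imputation by arm. There were 400 to 1,000 runs per cell. The entries are the overstatement of benefit in BDI-II points.

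| Missing | Dropout driven by Week 1 score: baseline and arm only | Same, exit score from all leavers | Dropout driven by Week 2 response: baseline and arm only | Same, exit score from all leavers |
|---|---|---|---|---|
| 11% | 0.7 | about 0 | 0.9 | 0.4 |
| 20% | 1.2 | about 0 | 1.6 | 0.8 |
| 29% | 1.7 | about 0 | 2.2 | 1.1 |

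With exit scores from half of the leavers, about half of the bias goes under the first mechanism and about a quarter under the second. Under the first mechanism, a sham slope half the active slope reduces the overstatement to roughly 0.3 to 0.8 points. With equal slopes it is about zero under either mechanism.

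**How strong the assumption is.** The completers' mean in an arm differs from the full-arm mean by d × gap, where d is the share missing and gap is how much worse leavers would score at Week 2 than those who stay. At 20% missing, 1.2 / 0.20 = 6 points and 1.6 / 0.20 = 8 points. The active arm must therefore lose people who are 6 to 8 points worse than those who stay, with no such gap in sham.

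**The case against.** The strongest reply is that the texts do not truly conflict. Assessments are due "any assessments planned for the subject on withdrawal from the clinical investigation, including adverse event collection, should be performed when intention to withdraw" is announced, and evaluations stop after that. Alternatively, 7.3.14 and the closing part of 7.3.15.1, which use the passive, cover withdrawal by staff, while the stopping sentence covers a subject's own decision. Both readings are tenable. The protocol states neither, and they give different instructions for voluntary leavers; the second produces exactly the selective gap described. The need to reconcile stands.

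A reader might also infer that exit scores will be lost or go unused. The documents do not support that. They say data up to withdrawal will be used, and they defer missing-data methods to the SAP. A sparse analysis model in 8.3 does not show that the imputation ignores Week 1 or exit scores. What can be said is that the protocol does not specify their use.

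The numbers need the same restraint, and these objections stand:

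- Near-complete removal of bias appears only when dropout is driven by the very score later used for imputation.
- The Day 7 BDI-II is scheduled, so someone leaving between Day 7 and Day 14 would normally already have a post-baseline score.
- Subjects lost to follow-up give no exit score under any wording, and the documents do not split them from announced withdrawals.
- Previous-trial non-completion is a Week 4 figure and was similar in the two arms. Nothing in the documents shows response-related dropout confined to the active arm, and subjects are blinded.

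**Conclusion.** The collection rules are inconsistent in the current text and should be reconciled. This part does not depend on any assumption, and the SAP cannot cure it, because a score that was not collected cannot be recovered.

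The effect on the primary result is conditional. About 0.7 to 2.2 points (0.6 to 1.9 planned standard errors) applies only if 11% to 29% are missing, they leave before Week 1, and leaving depends on response in the active arm alone. Exit scores from all leavers would remove between about half and nearly all of that, and proportionately less with partial capture. With equal dependence in both arms the bias is about zero. Only withdrawals before the Week 2 assessment matter for the primary endpoint. It would go too far to conclude that the trial's estimate is biased by any of these amounts, or that the previous trial's 41.5% is the Week 2 dropout rate to expect here.

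**What to change.** In 7.3.15.1, replace the stopping sentence with one rule consistent with 7.3.14 and 7.3.1. For example: *If a subject decides to withdraw, the subject is asked to complete the 7.3.14 assessments before evaluations stop, unless the subject refuses or rescinds consent.* This concerns outcome questionnaires only, not when treatment stops.

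In the standalone SAP, state that:

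- Week 1 and exit BDI-II scores, with their actual study day, inform the multiple imputation by arm.
- An exit score outside the Day 14 to 16 window is not itself a Week 2 value.

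Using the actual day is preferable to assigning each exit score to the nearest scheduled visit. A Day 12 score is nearest to Week 2 yet falls outside its window, and scores from the first days of use sit close to no scheduled visit.

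The cost is one protocol sentence, a short SAP paragraph and one more request to departing subjects. The questionnaires are already in ePRO.
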